11.3.4. Dressing Log Case Report Form

Dressing Log Case Report Form

MED-2018-DIV71-008: A case series evaluating a fibrillar collagen powder dressing to treat chronic, stalled lower-extremity wounds

Subject Number:	
Change #1 Date:	Secondary Dressing(s) Applied:
Change #2 Date:	Secondary Dressing(s) Applied:
Change #3 Date:	Secondary Dressing(s) Applied:
Change #4 Date:	Secondary Dressing(s) Applied:
Change #5 Date:	Secondary Dressing(s) Applied:
Change #6 Date:	Secondary Dressing(s) Applied:
Change #7 Date:	Secondary Dressing(s) Applied:
Change #8 Date:	Secondary Dressing(s) Applied:
Change #9 Date:	Secondary Dressing(s) Applied:
Change #10 Date:	Secondary Dressing(s) Applied:
Change #11 Date:	Secondary Dressing(s) Applied:
Change #12 Date:	Secondary Dressing(s) Applied:
Change #13 Date:	Secondary Dressing(s) Applied:
Change #14 Date:	Secondary Dressing(s) Applied:
Change #15 Date:	Secondary Dressing(s) Applied:

Fibrillar dressing for treating chronic, stalled wounds

MED-2018-DIV71-008

23 August 2018

V 1.0

CONFIDENTIAL

Dressing Log Case Report Form

MED-2018-DIV71-008: A case series evaluating a fibrillar collagen powder dressing to treat chronic, stalled lower-extremity wounds

Change #15 Date:	Secondary Dressing(s) Applied:
Change #16 Date:	Secondary Dressing(s) Applied:
Change #17 Date:	Secondary Dressing(s) Applied:
Change #18 Date:	Secondary Dressing(s) Applied:
Change #19 Date:	Secondary Dressing(s) Applied:
Change #20 Date:	Secondary Dressing(s) Applied:
Change #21 Date:	Secondary Dressing(s) Applied:
Change #22 Date:	Secondary Dressing(s) Applied:
Change #23 Date:	Secondary Dressing(s) Applied:
Change #24 Date:	Secondary Dressing(s) Applied:
Change #25 Date:	Secondary Dressing(s) Applied:
Change #26 Date:	Secondary Dressing(s) Applied:
Change #27 Date:	Secondary Dressing(s) Applied:
Change #28 Date:	Secondary Dressing(s) Applied:
Change #29 Date:	Secondary Dressing(s) Applied:
Change #30 Date:	Secondary Dressing(s) Applied:
Change #31 Date:	Secondary Dressing(s) Applied:

Fibrillar dressing for treating chronic, stalled wounds

MED-2018-DIV71-008

23 August 2018

V 1.0

CONFIDENTIAL

Dressing Log Case Report Form

MED-2018-DIV71-008: A case series evaluating a fibrillar collagen powder dressing to treat chronic, stalled lower-extremity wounds

Change #32 Date:	Secondary Dressing(s) Applied:
Change #33 Date:	Secondary Dressing(s) Applied:
Change #33 Date:	Secondary Dressing(s) Applied:
Change #34 Date:	Secondary Dressing(s) Applied:
Change #35 Date:	Secondary Dressing(s) Applied:
Change #36 Date:	Secondary Dressing(s) Applied:
Change #37 Date:	Secondary Dressing(s) Applied:
Change #38 Date:	Secondary Dressing(s) Applied:
Change #39 Date:	Secondary Dressing(s) Applied:
Change #40 Date:	Secondary Dressing(s) Applied:
Change #41 Date:	Secondary Dressing(s) Applied:
Change #42 Date:	Secondary Dressing(s) Applied:
Change #43 Date:	Secondary Dressing(s) Applied:
Change #44 Date:	Secondary Dressing(s) Applied:
Change #45 Date:	Secondary Dressing(s) Applied:
Change #46 Date:	Secondary Dressing(s) Applied:
Change #47 Date:	Secondary Dressing(s) Applied:

Fibrillar dressing for treating chronic, stalled wounds

MED-2018-DIV71-008

23 August 2018

V 1.0

CONFIDENTIAL

Dressing Log Case Report Form

MED-2018-DIV71-008: A case series evaluating a fibrillar collagen powder dressing to treat chronic, stalled lower-extremity wounds

Change #48 Date:	Secondary Dressing(s) Applied:
Change #49 Date:	Secondary Dressing(s) Applied:
Change #50 Date:	Secondary Dressing(s) Applied:
Change #51 Date:	Secondary Dressing(s) Applied:
Change #52 Date:	Secondary Dressing(s) Applied:
Change #53 Date:	Secondary Dressing(s) Applied:
Change #54 Date:	Secondary Dressing(s) Applied:
Change #55 Date:	Secondary Dressing(s) Applied:
Change #56 Date:	Secondary Dressing(s) Applied:
Change #57 Date:	Secondary Dressing(s) Applied:
Change #58 Date:	Secondary Dressing(s) Applied:
Change #59 Date:	Secondary Dressing(s) Applied:
Change #60 Date:	Secondary Dressing(s) Applied:
Change #61 Date:	Secondary Dressing(s) Applied:
Change #62 Date:	Secondary Dressing(s) Applied:
Change #63 Date:	Secondary Dressing(s) Applied:

Fibrillar dressing for treating chronic, stalled wounds

MED-2018-DIV71-008

23 August 2018

V 1.0

CONFIDENTIAL

**11.4. Adverse Event Form****Site/Subject Information**

Study Sponsor: Medline Industries, Inc.	Protocol Number: MED-2018-DIV71-008
Site Number:	Principal Investigator:
Subject Number:	

Adverse Event Information

#	Adverse Event:		Start Date: DD-MMM- YYYY	Stop Date: DD-MMM- YYYY	Ongoing:	Frequency:	Severity:	Outcome:	IP Lot #:	Relationship to IP:	Action Taken with IP:	SAE Status:	Comment:
		 Expected			 Yes							 Yes*	
		 Unexpected			 No								
		 Expected			 Yes							 Yes*	
		 Unexpected			 No								
		 Expected			 Yes							 Yes*	
		 Unexpected			 No								
Frequency:		Severity:		Outcome:			Relationship to IP:		Action Taken with IP:		SAE Status		
1 = Isolated 2 = Intermittent 3 = Continuous		1 = Mild 2 = Moderate 3 = Severe		1 = Resolved, with no sequelae 2 = Resolved, with sequelae 3 = Unresolved 4 = Death 5 = Unknown			1 = Not Related 2 = Possible 3 = Probable 4 = Definite		1 = None 2 = Modified 3 = Interrupted 4 = Discontinued		Death, life-threatening, prolonged hospitalization, significant disability/anomaly, medical intervention to prevent a serious outcome		
*In the event of a Serious Adverse Event, please complete the Serious Adverse Event Report form and send to Medline Industries, Inc. within 48 hours of awareness													

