7.2. Definition of Serious Adverse Event

The FDA definition of a Serious Adverse Event (SAE) will be used in this study: An AE or suspected adverse reaction is considered "serious" if, in the view of either the PI or Sponsor, it results in any of the following outcomes:

- Death
- A life-threatening adverse event
- Inpatient hospitalization or prolongation of existing hospitalization
- A persistent or significant incapacity or substantial disruption of the ability to conduct normal life functions or,
- A congenital anomaly/birth defect.

Important medical events that may not result in death, be life-threatening, or require hospitalization may be considered serious when, based upon appropriate medical judgment, they may jeopardize the participant and may require medical or surgical intervention to prevent one of the outcomes listed in this definition.

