7.6. Adverse Event Reporting

AEs will be recorded on the Adverse Event form (Appendix 11.4) by the PI. Changes in the severity of an AE will be documented to allow an assessment of the duration of the event at each level of severity. Changes in severity will necessitate a new CRF to document the new level of severity. AEs characterized as intermittent require documentation of onset and duration of each episode.

Non-serious AEs are to be reported to the study Sponsor on a weekly basis for review, and reported to the IRB per IRB reporting requirements.

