**11.5. Serious Adverse Event**

Site Information			
Study Sponsor: Medline Industries Inc.	Protocol Number: MED-2018-DIV71-008		
Site Number:	Principal Investigator:		
Site Address:	Report Type:	 Initial	
		 Follow-up	
		 Final	
Form Completed By:	Title:		
Telephone:	E-mail:		
Serious Adverse Event Information			
Subject Number:	Subject Initials:		
Birth Date:	Gender:	 Male	 Female
Investigational Product:			
Event Description: (Please include a detailed description of the event in question, including the results of any laboratory/diagnostic imagery testing)			
Site Notification of the Event:	Date Notified:	Time Notified:	
	Method of Notification:		
Event Qualifiers: (Check all that apply)	Start Date:	Stop Date:	 Ongoing
	 Death		 Intervention to Prevent Impairment
	 Life-Threatening		 Disability/Permanent Damage
	 Initial or Prolonged Hospitalization		 Congenital Anomaly
	 Other:		

Relevant Medical History:

Concomitant Medication/Device History: (Please include historical information such as medication/device name, dosage, frequency, route, start date, etc.)

Relationship to Investigational Product (IP):	 Not Related (event definitely not related to IP, as judged by the Principal Investigator)
	 Possibly Related (event maybe related to IP, as judged by the Principal Investigator)
	 Related (event definitely related to IP, as judged by the Principal Investigator)
Action Taken with Investigational Product:	 Discontinued- Please Provide Date:
	 Interrupted- Please Provide Date:
	 None

Comments:

Confirmation of Receipt: SECTION TO BE COMPLETED BY MEDLINE INDUSTRIES INC.	
Date Received:	Time Received:
Received By:	Title:

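### The SAE key on the adverse event form leaves out a new inpatient admission, which section 7.2 and the SAE form both count as serious

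*Combined protocol and SAP*

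**What the plan says.** Three places in the combined protocol and SAP state which hospital events make an adverse event serious.

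- **Section 7.2** (the definition): an event is serious if, "in the view of either the PI or Sponsor, it results in any of the following outcomes". The hospital item is "Inpatient hospitalization or prolongation of existing hospitalization".
- **Appendix 11.5** (the SAE form): the matching tick box reads "Initial or Prolonged Hospitalization".
- **Appendix 11.4** (the adverse event form): the key under SAE Status reads "Death, life-threatening, prolonged hospitalization, significant disability/anomaly, medical intervention to prevent a serious outcome".

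The reporting route depends on the classification. Section 7.6 says "AEs will be recorded on the Adverse Event form (Appendix 11.4) by the PI". If SAE Status is ticked, the asterisk leads to a footnote: "please complete the Serious Adverse Event Report form and send to Medline Industries, Inc. within 48 hours of awareness". Section 7.7 requires the SAE form to reach both the sponsor and the reviewing IRB within 48 hours of the investigator learning of the event. It gives the sponsor 10 working days from its own first notice to report its evaluation to FDA and the IRBs. For the other route, 7.6 says "Non-serious AEs are to be reported to the study Sponsor on a weekly basis for review", and that these events are "reported to the IRB per IRB reporting requirements".

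**The concern.** The 11.4 key is printed where an event is sorted into serious or non-serious. The SAE form carries the full hospital criterion, but it is opened only after an event has been classed as serious, so it cannot correct the first sorting.

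The item left out matters in this setting. Participants attend an outpatient podiatry clinic (4.1), and a prolonged stay presupposes that someone is already in hospital. For an outpatient, the first hospital event would ordinarily be a new admission. That is a reasonable inference from the setting only, because the documents give no admission rate.

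At stake is the timeliness of safety reporting. A new admission that the site treats as non-serious would travel on the weekly route, and the sponsor's 10-working-day clock would start later as well.

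**Working it through.** The plan states no figure for this point, so there is none to reproduce. The check has two steps.

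**Step 1: compare the criteria.** Here the hospital item of 7.2 is split into its two parts.

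| Outcome | 7.2 | 11.4 key | 11.5 form |
|---|---|---|---|
| Death | yes | yes | yes |
| Life-threatening event | yes | yes | yes |
| New inpatient admission | yes | **not listed** | yes |
| Longer stay for someone already admitted | yes | yes | yes |
| Lasting incapacity | yes | yes, in a combined disability/anomaly item | yes |
| Congenital anomaly | yes | yes, if the same combined item is read that way | yes |
| Important medical event needing intervention | yes | yes, as an intervention item | yes, as an intervention item |

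The clear gap is the new admission. It is missing from the key and present in both other places.

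**Step 2: timing, if a new admission is sent by the non-serious route.** Inputs:

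- SAE limit: 48 h from awareness (7.7, repeated in the 11.4 footnote).
- Non-serious reports to the sponsor: weekly (7.6). Assumption: this means at most 7 days from awareness, so 7 x 24 = 168 h.
- Non-serious reports to the IRB: no interval given (7.6).

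Let t be the time from awareness to the next weekly report, between 0 and 168 h. The excess over the SAE limit for the sponsor's first notice is max(0, t - 48).

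- Smallest: 0 h, when the weekly report falls within 48 h of awareness.
- Largest: 168 - 48 = 120 h, and 120 / 24 = 5 days.

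The 10-working-day clock in 7.7 starts at the sponsor's first notice. Its start could therefore fall up to 120 h later than the latest start under the 48-hour rule.

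Two delays cannot be bounded from the documents. A line in a weekly non-serious report is not an SAE form, so that form would follow only once someone reclassified the event. The IRB delay depends on that IRB's own rules, which the documents do not give.

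If the key matched 7.2, a new admission would fall under the 48-hour route and the excess attributable to the key would be 0 h.

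**The case against.** The strongest reply is that the key is only shorthand and that harm is remote.

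- Section 7.2 is the definition. The footnote is triggered by a serious adverse event as such and does not redefine one.
- The PI records the events on this form and reviews them (9.3.2). Either the PI or the sponsor can judge an event serious.
- The key's intervention item could capture some new admissions.
- Section 7.3 places the phrase prolonged hospitalization in brackets after a reference to additional hospitalization, which suggests loose wording rather than a deliberately narrower rule.

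Most of this stands, and it makes the consequence conditional. It does not remove the mismatch. Section 7.3 grades severity, not seriousness. The intervention item need not cover every admission. The PI's review is made by the person who fills in the form, the sponsor sees non-serious events weekly, and routine monitoring may be two months apart (9.2). The last two checks can act after the 48 hours have passed.

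A reader might also infer more than the documents support:

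- **That the form changes what counts as an SAE.** It does not; a site applying 7.2 reports on time.
- **That SAE reports will be up to five days late.** The 120 h is a worst case for the sponsor's first notice alone, in a case already misrouted. It is neither an expected delay nor a limit on the delay to the SAE form or the IRB.
- **That a score of six outcomes out of seven measures the gap.** Section 7.2 prints five bullets and a paragraph on important medical events. Seven arises only by splitting one bullet, and six only by crediting the key's combined disability/anomaly item with two outcomes. The evidence is the missing criterion, not the count.

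**Conclusion.** The inconsistency is real and certain as a matter of wording: the 11.4 key omits a new inpatient admission, which 7.2 and 11.5 include. It should be corrected because it sits on the form used to sort events.

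The consequence is conditional. It requires a site to follow the printed key rather than 7.2, and the admission not to be caught by the intervention item. In that case the sponsor's first notice would be between 0 and 120 h (5 days) past the 48-hour limit, taking weekly as at most 7 days from awareness. No probability, admission rate or expected number of events can be drawn from the documents. No efficacy analysis is affected.

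A separate coding point adds no weight to this one. Section 7.4 and the 11.4 form have four relatedness categories, while the 11.5 form has three boxes and none for a probable relationship. The adverse event form still records that category, so only the coding between the two forms is affected.

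**What to change.** Reconcile the SAE Status key in 11.4 with 7.2 and 11.5 by replacing its prolonged-hospitalization item with the protocol's own wording, "Inpatient hospitalization or prolongation of existing hospitalization". This changes one phrase on one form and needs no new data, visits or procedures.

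As a separate tidy-up, give the SAE form the four relatedness categories of 7.4, which changes one set of boxes.

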**11.5. Serious Adverse Event**

Site Information			
Study Sponsor: Medline Industries Inc.	Protocol Number: MED-2018-DIV71-008		
Site Number:	Principal Investigator:		
Site Address:	Report Type:	 Initial	
		 Follow-up	
		 Final	
Form Completed By:	Title:		
Telephone:	E-mail:		
Serious Adverse Event Information			
Subject Number:	Subject Initials:		
Birth Date:	Gender:	 Male	 Female
Investigational Product:			
Event Description: (Please include a detailed description of the event in question, including the results of any laboratory/diagnostic imagery testing)			
Site Notification of the Event:	Date Notified:	Time Notified:	
	Method of Notification:		
Event Qualifiers: (Check all that apply)	Start Date:	Stop Date:	 Ongoing
	 Death		 Intervention to Prevent Impairment
	 Life-Threatening		 Disability/Permanent Damage
	 Initial or Prolonged Hospitalization		 Congenital Anomaly
	 Other:		

Relevant Medical History:

Concomitant Medication/Device History: (Please include historical information such as medication/device name, dosage, frequency, route, start date, etc.)

Relationship to Investigational Product (IP):	 Not Related (event definitely not related to IP, as judged by the Principal Investigator)
	 Possibly Related (event maybe related to IP, as judged by the Principal Investigator)
	 Related (event definitely related to IP, as judged by the Principal Investigator)
Action Taken with Investigational Product:	 Discontinued- Please Provide Date:
	 Interrupted- Please Provide Date:
	 None

Comments:

Confirmation of Receipt: SECTION TO BE COMPLETED BY MEDLINE INDUSTRIES INC.	
Date Received:	Time Received:
Received By:	Title:

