7.4. Relatedness of Adverse Event and Serious Adverse Event

- **Unrelated:** This category applies to those adverse events which, after careful consideration, are clearly and incontrovertibly due to extraneous causes (disease, environment, etc.)
- **Possible:** This category applies to those adverse events for which, after careful medical consideration at the time they are evaluated, a connection with the Investigational Product administration appears unlikely but cannot be ruled out with certainty.
- **Probable:** This category applies to those adverse events which, after careful medical consideration at the time they are evaluated, are felt with a high degree of certainty to be related to the Investigational Product.
- **Definite:** This category applies to those adverse events which, after careful consideration, are clearly and incontrovertibly due to the Investigational Product.

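### The SAE form grades relatedness on three levels with no Probable box, while section 7.4 and the AE form use four; section 7.4 also has no level between unlikely and highly certain

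*Combined protocol and SAP*

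**What the plan says.** Section 7.4 is headed "Relatedness of Adverse Event and Serious Adverse Event", so one scale is meant to serve both kinds of event. It has four levels:

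- Unrelated: events that "are clearly and incontrovertibly due to extraneous causes (disease, environment, etc".)
- Possible: events for which "a connection with the Investigational Product administration appears unlikely but cannot be ruled out with certainty".
- Probable: events that "are felt with a high degree of certainty to be related to the Investigational Product".
- Definite: events that "are clearly and incontrovertibly due to the Investigational Product".

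The AE form (11.4) carries four codes without definitions: "1 = Not Related 2 = Possible 3 = Probable 4 = Definite".

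The SAE form (11.5) has three boxes. The lowest is Not Related, explained as definitely not related. The middle one is "Possibly Related (event maybe related to IP, as judged by the Principal Investigator"). The highest is "Related (event definitely related to IP, as judged by the Principal Investigator"). There is no Probable box.

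The AE form has an SAE status column, and its footnote sends the site on to the SAE form when an event is serious. Section 7.7 requires the SAE form to reach the sponsor and the IRB within 48 hours.

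**The concern.** A causality grade is useful only if the same judgement gives the same grade wherever it is recorded. Here a serious event is graded twice, on scales with different numbers of levels and with one shared word defined differently. The investigator can follow every instruction and still produce two records of one event that do not agree, with nothing to say which prevails.

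The investigator's judgement is the main causality record. Section 9.3.2 has the investigator review AEs and SAEs and make safety determinations. Section 7.7 has the sponsor evaluate each SAE and report the result to FDA and the IRBs within 10 working days. Section 9.3.5 allows AE review to support suspension or termination. Section 9.3.3 has the monitor check CRFs against source. Anyone doing this work for a Probable SAE would find that the form sent to the sponsor cannot show the grade on the AE form.

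The second problem lies inside 7.4 and does not depend on the SAE form: the scale has no place for an event that is plausibly, but not almost certainly, due to the powder.

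**Working it through.** No figure in the plan is involved and no arithmetic applies beyond counting levels: four in section 7.4, four on the AE form, three on the SAE form. The check sets the three scales side by side.

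| Section 7.4 | Meaning in 7.4 | AE form 11.4 | SAE form 11.5 | Match in meaning? |
|---|---|---|---|---|
| Unrelated | Clearly extraneous | 1, Not Related | Not Related: definitely not | Yes; the label in 7.4 differs |
| Possible | Unlikely, not excluded | 2, Possible | Possibly Related: maybe | Similar name, different definition |
| Probable | High certainty of relation | 3, Probable | None | No |
| Definite | Clearly due to the product | 4, Definite | Related: definitely | Yes; the SAE label differs |

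**Step 1: is one event graded on both scales?** Yes. By 7.2 an SAE is an AE that meets a seriousness criterion, 7.6 puts AEs on the AE form, and that form's footnote adds the SAE form for serious events.

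**Step 2: is there a conversion rule?** None appears in 7.4 to 7.7, on either form, or elsewhere in the documents supplied.

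**Step 3: what happens to a Probable SAE?** Only two boxes are open. Entered as Related, it is recorded as definite, which overstates the 7.4 grade. Entered as Possibly Related, it is recorded as maybe. It then shares a box with an SAE whose 7.4 grade is Possible, because the lowest box demands that the event be definitely not related and so cannot take an unlikely one. In that case the middle box holds both unlikely and highly certain events.

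**Step 4: is the 7.4 scale complete in itself?** In order, its levels are clearly not, unlikely, highly certain, clearly yes. An event the investigator thinks may well be related, without high certainty, is above Possible and below Probable. The middle box of the SAE form would describe it, but the scale that is supposed to govern that form does not. Redness around the wound is an example: section 2.3.1 names irritation or reddening as the study risk, and section 2.2 adds a secondary dressing for every participant and compression for venous ulcers, so attribution to the powder may be plausible but uncertain. This example shows the gap in 7.4 only. Redness would ordinarily be non-serious and go on the AE form alone, so it would not be graded twice.

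**The case against.** The strongest case on the other side is that nothing operational turns on the grade. That is correct.

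- **Expectedness.** Section 7.5 compares the kind, severity and frequency of the event with the known risk information. Relatedness is not a criterion.
- **Reporting.** Section 7.7 sends every SAE to the sponsor and IRB whatever its relatedness, and 7.6 sends all non-serious AEs to the sponsor weekly and to the IRB under its own rules. No event goes unreported and no deadline moves because of the missing box.
- **Analysis.** Section 8 contains no safety tabulation and no analysis by relatedness, so no planned result changes.

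A reader might still infer that, with 20 participants, one recoded event would move the number of related SAEs between 0 and 1 and so alter the safety conclusion. The documents do not support that. They plan no such count and do not say what would count as related. If anything other than Not Related counts, a Probable SAE counts whichever box is ticked. Only if the Related box alone counts does the choice matter. The documents also give no expected SAE rate.

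Two further objections stand in part. The Probable grade is not lost, because it stays on the AE form, and the SAE form has free-text fields that could explain it. But the coded entry on the form sent to the sponsor and IRB still differs. One could also argue that a Probable event is by elimination Possibly Related, since it is not definite. That reading is reasonable, but it is not written down, and it groups highly certain events with unlikely ones.

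**Conclusion.** The inconsistency is real and follows from the text alone. An SAE graded Probable under 7.4 cannot be recorded faithfully on the SAE form, and possible means two different things in the two places. Separately, 7.4 leaves plausibly related events of any seriousness without a fitting level.

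The effect is confined to the consistency of the recorded causality judgement and of what the sponsor evaluates. It does not reach expectedness, reporting duties or any section 8 analysis. Its size cannot be given as a number: the missing box affects every SAE graded Probable, which may be none, and the gap in 7.4 affects every AE or SAE of intermediate plausibility. The conclusion assumes that SAEs are entered on both forms, as the AE form directs, and that no conversion rule exists outside the documents supplied. The point does not threaten the study, but it should be corrected because following the documents exactly can produce a miscoded grade.

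**What to change.** 1. Replace the three boxes on the SAE form with the four levels of section 7.4 and the AE form.
2. Reword Possible in 7.4 so that it covers events that may be related, filling the space below Probable. The sponsor can choose whether events judged unlikely get a level of their own or join the lowest level. If they join the lowest level, its definition must be loosened to admit them.
3. Use the same labels and definitions in 7.4, 11.4 and 11.5, including one name for the lowest level, which is now Unrelated in 7.4 and Not Related on the forms.

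A stated conversion rule would be a weaker alternative. It would settle which box a Probable SAE takes but would leave the gap in 7.4.

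The cost is wording in one protocol section and on two forms. No visit, measurement, analysis or sample size changes.
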